6.5.1 Baseline Data

Descriptive statistics will be used to characterize baseline measures in subjects.

6.5.2 Efficacy Analysis

As a general strategy, continuous endpoints will be summarized using the five-number summary (mean, standard deviation, median, minimum, and maximum). Categorical endpoints will be summarized using frequency distributions.

Subgroup analyses may also be performed to further delineate study data. These analyses may include t-tests, Wilcoxon rank-sum tests, and Pearson correlation/Spearman correlation for continuous measures; for categorical variables, chi-square and Fisher's exact tests may also be performed, as appropriate.

This is a pilot study to generate data to assess feasibility of study design/procedures and for formal sample size estimation for a larger study of the efficacy of the bihormonal bionic pancreas in children and adults with hyperinsulinism and post-pancreatectomy diabetes. The sample size for this pilot study may be too small to detect statistical significance, however, we offer the following plan for analysis of the outcomes for this study.

Mean CGMS-measured glucose concentration (calculated as the mean of all CGMS-measured concentrations [measured every 5 min] over the study period) and the mean proportion of time when the CGMS-measured glucose concentration was < 60 mg/dL during the last 3 days on the bionic pancreas will be compared to the same outcomes during the control period by paired-sample Student's t-test (or Wilcoxon signed rank test if data is not normally distributed) to determine if the intervention conferred an improvement in glycemic control. Secondary outcomes will be analyzed with univariate analysis.

6.5.3 Safety Analysis

Safety will be assessed through an examination of the incidence, severity, and type of treatment-emergent adverse events and changes in vital signs, physical examination results, glucose monitoring, and use of concomitant medications and concomitant treatment from baseline to specified time points throughout the trial. All subjects entered study at either admission will be included in the safety analysis. The frequencies of AEs by type, body system, severity and relationship to study device will be summarized. SAEs (if any) will be described in detail. Safety variables will be assessed by comparison of frequency of adverse events (AEs) and serious adverse events (SAEs) during the two study periods.

6.6 Sample Size and Power

The proposed sample size of 10 subjects for this pilot study is a sample of convenience based on the number of subjects that we can feasibly study during one year and with the funds available. The study may not be powered to achieve statistically significant differences between the bihormonal bionic pancreas study period and the standard care period, but the data from this pilot study will be used for formal sample size estimation for a larger study. However, we offer the following sample size considerations based on previous studies in children and adolescents with type 1 DM.

The two co-primary outcomes are (1) mean glucose concentration as measured by the CGMS during the final 3 days of each admission, and (2) the mean proportion of time that the CGMS-measured glucose concentration was less than 60 mg/dL during the same periods. In children and adolescents with type 1 DM, the use of the bionic pancreas was associated with a lower mean CGMS-measured glucose compared to standard pump therapy (137 ± 11 mg/dL vs. 167 ± 31 mg/dL, $p=0.00037$) and a lower proportion of time with a CGMS-measured glucose concentration below 60 mg/dL ($1.2 \pm 1.1\%$ vs. $2.8 \pm 1.2\%$, $p<0.0001$)⁶. The standard deviation of the difference will depend on the within-subject correlation r in this crossover study design. If we assume that the standard deviation of both groups would be the same as above the following table shows the sample size needed to detect a similar difference (an effect size of 1.2 and 2, respectively) with an alpha of 0.05 and a power of 0.8 for different values of r .

6.6.1 Mean CGMS-measured glucose

| r | Sample size ($1-\beta=0.8$) |
|-------|----------------------------------|
| 0.001 | 12 |
| 0.01 | 12 |
| 0.05 | 12 |
| 0.1 | 11 |
| 0.2 | 11 |
| 0.3 | 10 |
| 0.4 | 10 |
| 0.5 | 9 |

6.6.2 Proportion of time with a CGMS-measured glucose concentration below 60 mg/dL

| r | Sample size (1- β =0.8) |
|-------|----------------------------------|
| 0.001 | 11 |
| 0.01 | 11 |
| 0.05 | 10 |
| 0.1 | 10 |
| 0.2 | 9 |
| 0.3 | 8 |
| 0.4 | 8 |
| 0.5 | 7 |

6.7 Interim Analysis

This is an open label study. Safety data will be examined on an ongoing basis to ensure safety of the study subjects.

7 DRUGS/DEVICES

7.1 Drugs

The study involves subcutaneous administration of insulin lispro (Humalog®, Lilly) or insulin aspart (Novolog®, Novo Nordisk); and rDNA-origin glucagon for injection (Glucagon™, Lilly). All are commercially available by prescription and are indicated for patients with diabetes, but not for use in a bionic pancreas. Subjects will use their usual rapid-acting insulin analog during the usual care arm of the study and during the bionic pancreas arm. The study also involves subcutaneous administration of glucagon for injection, which is indicated for the treatment of severe hypoglycemia, but not for use in a bionic pancreas.

The control system can administer bolus doses of each drug up to every five minutes. A single automated bolus of insulin will not exceed 3 units per 5-minute dose [30 μ l] and a single meal-priming dose, which is triggered by the user, will not exceed 12 units [120 μ l]. A single bolus of glucagon will not exceed 80 μ g [80 μ l]. The insulin pumps can administer as little as 0.5 μ l (0.05 units of U-100 insulin or 0.5 μ g of 1 mg/ml glucagon) in single programmable bolus doses.

It is expected that the total daily dose of glucagon will be < 1.5 mg daily as in previous studies. The mean daily glucagon dose in the previous outpatient study was 0.72 mg/day (range 0.22-1.34 mg/day). The recommended dose of glucagon for patients suffering from severe hypoglycemia is 1 mg as a single injection. Mean glucagon levels in the previous inpatient studies have been above the normal fasting range for glucagon only 1% of the time. Therefore, the glucagon exposure of subjects is expected to be modest.

7.2 Devices

7.2.1 Personal Insulin Pumps

Subjects will retain and wear their personal insulin pumps for the Control Admission. There will be no intervention to the subjects' insulin pumps as part of this study, except for them being removed during the Bihormonal Bionic Pancreas Admission of this study.

7.2.2 Bionic Pancreas System

Infusion sets: Subjects will wear two FDA approved commercially available infusion sets, one for insulin infusion and one for glucagon infusion, when applicable. Infusion sets that are compatible with the Tandem® t:slim™ insulin pump (leur lock connection) will be used during the bionic pancreas phase that are similar to the infusion sets they use during the control phase. If an infusion set falls off or is clinically suspected of failing, it will be replaced with a new one. The insulin infusion set will be changed at least every 48 hours; the glucagon infusion set will be changed every 24 hours.

Bionic Pancreas Control Unit: The Beta Bionics mobile application that runs the control algorithm and the Dexcom® G5® app are both installed on a stock iPhone® 6s running iOS 10. The Betabionics app receives the CGM glucose values that are captured by the Dexcom® G5® app.

The control algorithm app has a graphical user interface (GUI) that displays the current Dexcom® CGM glucose, a graphical history of the Dexcom® CGM glucose, and doses of insulin and glucagon delivered by the control algorithm. The GUI can also be used to input meal announcements, designating the size of the meal as larger than typical, typical in size, smaller than typical, or just a bite, and the type of meal as breakfast, lunch, or dinner. This will trigger a partial meal-priming bolus the size of which will adapt during the trial to meet a target of 75% of the insulin needs for that size and type of meal.

The target glucose level in the bionic pancreas will be programmed by the study staff prior to the start of each admission. This will be locked and the subject will be unable to accidentally change or tamper with this setting. Subjects will be aware of what their glucose target is.

The GUI can also be used to manage meal boluses as usual, and will administer correction boluses in response to entered BG values, during periods when the Dexcom® CGM is offline, such as the period after a sensor is replaced and before the new sensor has been calibrated. During these times the control algorithm will determine and direct the administration of insulin basal rates either based on the subject's weight early in the experiment, or on the average of adaptively determined basal rates for that time of day once sufficient experience has been accumulated (i.e. 24 hours or more) by the control algorithm. The controller will also administer insulin and/or glucagon as appropriate in response to any entered BG values, just as if they were Dexcom® CGM values.

The GUI also displays local audio and visual alarms if communication is dropped between the Dexcom® CGM transmitter and the bionic pancreas control unit or between the control unit and the two insulin pumps. The Dexcom® CGM also has its own hard-coded alarm

distinct from the bionic pancreas when the CGM glucose crosses below 55 mg/dl. These alarms may be configured so that they require the entry of a code to dismiss.

The iPhone® communicates wirelessly via the Bluetooth Low Energy (BTLE) protocol with up to two Tandem® t:slim™ insulin pumps to deliver insulin and glucagon.

In all configurations, if communication failures between the Dexcom® CGM and the bionic pancreas or the bionic pancreas and the cloud are not resolved within 15 minutes they trigger alerts to study staff who will then contact the wearer according to study protocol. If communication failure between the bionic pancreas and pumps is not resolved within 15 minutes this triggers and alert to study staff who will contact the wearer. Also in both configurations, if the Dexcom® CGM glucose drops below 50 mg/dl and the user does not enter a BG into the bionic pancreas GUI within 15 minutes, this will trigger an alert to study staff, who will then contact the wearer according to the study protocol. Monitoring will be the same in all study arms.

Tandem® t:slim™ Pumps: These pumps are FDA approved insulin pumps with reservoirs capable of holding 300 units (3 ml) of insulin or 3 ml of a glucagon solution. The pumps have a mechanical dosing resolution of 1/120 (0.00833) unit and can deliver liquids at a maximal rate of ~ 33 µl per minute (2 ml per hour). They are slave to the bionic pancreas control unit and are controlled wirelessly via the Bluetooth Low Energy protocol by the iPhone® 6S.

7.2.3 Continuous Glucose Monitoring System

During each admission, a Dexcom® G5® continuous glucose monitor system (CGMS) will be placed to measure glucose concentration continuously. The CGMS will be calibrated twice daily before breakfast and dinner and as requested by the CGMS. During Control Admission, the CGMS will be connected to an iPhone® to allow remote monitoring. During Experimental Admission, the CGMS will be part of the bionic pancreas system and will provide input to the controller. The sensor is powered by the battery within the transmitter that clips to the sensor and the whole assembly is held to the skin with an adhesive patch and communicates wirelessly with the CGMS receiver. If the CGMS sensor fails for any reason during the experiment it will be replaced promptly.

Prior to any reuse of the CGM transmitter between patient admissions, study staff will thoroughly clean and disinfect the transmitter according to the manufacturer's best practices (detailed instructions included in the Dexcom® User Guide).

7.2.4 Bedside Glucometer

Capillary glucose will be monitored before each meal, at bedtime, at least once overnight and PRN (Nova StatStrip® point-of-care glucose monitor, Nova Biomedical Corporation, Waltham, MA).

7.2.5 Drug Accountability

For this study, patients will be administered rDNA-origin glucagon for injection (Glucagon™, Lilly) via the Bionic Pancreas. Dosage is 1 mg/mL; route of administration is subcutaneous. The glucagon drug supply for this study will be purchased from

Investigational Drug Service at The Children's Hospital of Philadelphia. Drug will be dispensed by Investigational Drug Service following prescription by the Investigator or her medically-licensed designee and may not be used for any purpose other than that described in this protocol. At study completion, all drug supplies, including partially used and empty containers, will be disposed of according to manufacturer recommendations.

Adequate records of study drug purchase and dispensation will be maintained by the CHOP Investigational Drug Service. Records of investigational drug orders, dispensing records, and disposition forms may be examined during the course of the study.

8 SAFETY MANAGEMENT

8.1 Preexisting Condition

A preexisting condition is one that is present at the start of the study. A preexisting condition will be recorded as an adverse event if the frequency, intensity, or the character of the condition worsens during the study period.

8.2 General Physical Examination Findings

At screening, any clinically significant abnormality will be recorded as a preexisting condition. At the end of the study, any new clinically significant findings/abnormalities that meet the definition of an adverse event will also be recorded and documented as an adverse event.

8.3 Clinical Adverse Events

Clinical adverse events (AEs) will be monitored throughout the study.

8.4 Definition of an Adverse Event

An adverse event is any untoward medical occurrence in a subject who has received an intervention (drug, biologic, or other intervention). The occurrence does not necessarily have to have a causal relationship with the treatment. An AE can therefore be any unfavorable or unintended sign (including an abnormal laboratory finding, for example), symptom, or disease temporally associated with the use of a medicinal product, whether or not considered related to the medicinal product.

All AEs (including serious AEs) will be noted in the study records and on the case report form with a full description including the nature, date and time of onset, determination of non-serious versus serious, intensity (mild, moderate, severe), duration, causality, and outcome of the event.

8.5 Adverse Event Reporting

Unanticipated problems related to the research involving risks to subjects or others that occur during this study (including SAEs) will be reported to the IRB in accordance with CHOP IRB SOP 408: Unanticipated Problems Involving Risks to Subjects. AEs that are not serious but that are notable and could involve risks to subjects will be summarized in narrative or other format and submitted to the IRB at the time of continuing review.

8.5.1 Reporting Hypoglycemia and Hyperglycemia Adverse Events

To maintain consistency across protocols under the Bionic Pancreas IDE, we have consulted with the team who holds the IND at Boston University and our clinical trial collaborators at Massachusetts General Hospital to determine appropriate and consistent methods for reporting the expected adverse events of hypoglycemia and hyperglycemia. Study team will report hypoglycemia and hyperglycemia if they meet the threshold of a severe adverse event. Hypoglycemia and hyperglycemia will be reported in line with CHOP and FDA requirements (and GCP guidelines) requirements for reporting serious adverse events.

Specifically, hypoglycemia will be reported if a patient experiences hypoglycemia that results in a compromised neurologic status to the extent that the patient requires assistance to treat, including seizure or loss of consciousness. Hyperglycemia will be reported as an AE if it is prolonged and associated with replacing the infusion set, or removing the BP and giving correction insulin. Additionally, hyperglycemia will be recorded as an AE if the subject mounts ketones > 0.6 mmol/L. Hyperglycemia will be recorded as a serious adverse event if the subject becomes diabetic-ketoacidotic.

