 - The first step in responding to hyperglycemia according to the CGMS will be to perform a fingerstick BG measurement. If the BG measurement is not consistent with the CGMS, the CGMS will be calibrated as long as there has been no carbohydrate intake in the last 30 minutes and there is no steep rise or fall in glucose (>2 mg/dL/min). If a calibration is delayed for this reason, it will be performed at the next opportunity. If the BG measurement is consistent with the CGMS, the insulin infusion site will be investigated and replacement will be considered.
 - If there is a complete failure of bionic pancreas operation and it is anticipated that restarting it will take more than an hour, subjects may take over their own BG control using their own insulin pump or with insulin injections until the bionic pancreas can be brought back online with the help of study staff. During the day, this should be rare. If the failure occurs at night, every effort should be made to correct the problem as soon as possible, which should almost always be possible within 12 hours.
 - If a CGMS sensor fails during the course of an experiment, the system will provide basal insulin based on past requirements and will allow announcement of meals and entry of fingerstick BG measurements, which will be treated as CGMS data and may result in administration of insulin and/or glucagon. The CGMS sensor will be replaced as soon as possible and normal bionic pancreas control will resume when the new sensors is calibrated.
 - Subjects will be asked to announce the three major meals of the day, but not snacks, to the bionic pancreas. The meal announcement will consist of choosing the type of meal (breakfast, lunch, dinner) and the size of the meal relative to typical meals for that subject (snack, smaller than typical, typical, larger than typical).
 - The insulin infusion set and reservoir will be changed at least every two days.
-

- The glucagon reservoir will be replaced every day. Each reservoir will be filled with two vials of freshly reconstituted Lilly glucagon. The glucagon infusion set will be changed daily with the reservoir change.
- On days when both the insulin and glucagon reservoirs will be changed, they will be changed at different times in the day, separated by at least one hour. The infusion sets and tubing will be labeled to avoid confusion or cross connection.

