4.5.3 Discharge

- Bionic pancreas will be disconnected and the subject will be asked to connect and initiate home insulin pump.
- Meters and the bionic pancreas will be downloaded.
- The body weight of the subject will be documented.
- Physical exam prior to hospital discharge.
- Subjects will be discharged on the fourth day or afterward if the subject requires additional time to transition back to his/her home regimen. Prior to discharge, subjects must have a recent history and glucose trajectory that is sufficiently stable for safe discharge in the judgment of a study provider.

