6.5 Statistical Methods

Only data from subjects that complete both study periods will be included in the analysis. In patients that complete the study, the primary analysis of the designated endpoints will be calculated on an intention-to-treat basis, including data from periods when the bionic pancreas was not in use, if available (CGMS data may not be available in some failure

modes). We may also perform secondary, exploratory analyses excluding bionic pancreas down-time, since this may better represent the performance possible with a fully integrated system. We will calculate percentages, means, standard deviations, and ranges in descriptive analyses. We will use paired t-test for comparison of means. In a secondary analysis, we will look for any period effect and any interaction between treatment and period, although no such interaction is predicted and there is probably insufficient power to identify a small interaction. We may, in exploratory analyses, also stratify subjects for secondary analyses of the pre-specified endpoints by the following characteristics: sex, age, usual care insulin total daily dose, body mass index, A1c, and use of CGMS in usual care.

The following populations are defined for the analysis and reporting of data.

- All Subjects as Treated (AST): All subjects who had the bihormonal artificial pancreas placed for any period of time. This population will be used for assessment of safety and tolerability.
- Per-Protocol (PP): The set of data generated by subjects who received protocol procedures sufficiently to ensure that these data will be likely to exhibit the effects of treatment, according to the underlying scientific model.

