8.6 Definition of a Serious Adverse Event (SAE)

An SAE is any adverse drug experience occurring at any dose that results in any of the following outcomes:

- death,
- a life-threatening event (at risk of death at the time of the event),
- requires inpatient hospitalization or prolongation of existing hospitalization,
- a persistent or significant disability/incapacity, or
- a congenital anomaly/birth defect in the offspring of a subject.

Important medical events that may not result in death, be life-threatening, or require hospitalization may be considered a serious adverse drug event when, based upon appropriate medical judgment, they may jeopardize the subject and may require medical or surgical intervention to prevent one of the outcomes listed in this definition.

A distinction should be drawn between serious and severe AEs. A severe AE is a major event of its type. A severe AE does not necessarily need to be considered serious. For example, nausea which persists for several hours may be considered severe nausea, but would not be an SAE. On the other hand, a stroke that results in only a limited degree of disability may be considered a mild stroke, but would be an SAE.

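### The planned between-admission AE comparison includes a hyperglycemia criterion that only the device admission can meet, and sections 6.5 and 6.5.3 name conflicting safety sets

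*Combined protocol and SAP*

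**What the plan says.** Section 6.5.3 sets out the comparison: "Safety variables will be assessed by comparison of frequency of adverse events (AEs) and serious adverse events (SAEs) during the two study periods". It states no test and no denominator.

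Section 8.5.1 defines when hyperglycemia counts. It is an AE if it is "prolonged and associated with replacing the infusion set, or removing the BP and giving correction insulin". It is also an AE if ketones exceed 0.6 mmol/L, and an SAE if DKA develops.

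Two sections name the safety set. Section 6.5 defines All Subjects as Treated (AST) as "All subjects who had the bihormonal artificial pancreas placed for any period of time" and adds: "This population will be used for assessment of safety and tolerability". Section 6.5.3 says instead: "All subjects entered study at either admission will be included in the safety analysis".

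**The concern.** A comparison of event counts between two periods is interpretable only if the same clinical course would be counted in either period, and if the same rule decides who contributes. Neither condition is fully met here.

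The BP-removal limb of the hyperglycemia rule can be satisfied only while the subject is on the BP. A prolonged episode handled in standard care with correction insulin alone, without a set change and without raised ketones, is not an AE under section 8.5.1. An episode handled on the device by removing it and giving correction insulin is.

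The AST rule can remove standard-care subjects and their events but never device subjects. Both features push the same way: relatively more AEs attributed to the device admission. With 10 to 12 subjects, one or two events classified differently could change how the tolerability of the device is read for the larger study.

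**Working it through.** The plan gives no AE rate and no safety power calculation, so there is no stated figure to reproduce. The check takes each trigger and each population rule in turn, then bounds the size.

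**Step 1. Which triggers depend on the device?**

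| Trigger | Source | Possible in standard care? |
|---|---|---|
| Prolonged hyperglycemia with infusion set replacement | 8.5.1 | Yes. 4.9.2 has the site and the pump or BP checked above 300 mg/dL in either admission |
| Prolonged hyperglycemia with BP removal and correction insulin | 8.5.1 | No |
| Ketones > 0.6 mmol/L | 8.5.1 | Yes. 4.9.2 collects beta-hydroxybutyrate above 240 mg/dL without limiting it to one admission |
| DKA (SAE) | 8.5.1 | Yes |
| Hypoglycemia with neurologic compromise needing assistance | 8.5.1 | Yes |
| General AE and SAE definitions | 8.4, 8.6 | Yes. Neither names the BP |

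One limb of one non-serious AE rule is specific to the device admission. The set-replacement limb is open to both, but the prompts differ. Section 4.5.2, which covers the device admission only, says that after a confirmed high CGMS reading "the insulin infusion site will be investigated and replacement will be considered", with no threshold given. Section 4.4.2 has no such step for standard care, which leaves the 300 mg/dL check in 4.9.2.

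**Step 2. Size of the definitional effect (illustration).** Assume:
- N = 12 admissions per condition and the same true rate p = 0.20 of prolonged hyperglycemia per admission;
- a share q of episodes would be met only by the BP-removal limb, with no set change and no ketones > 0.6 mmol/L;
- all other episodes are counted alike in both admissions.

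Neither p nor q is in the documents.

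Expected counted events: device = N × p; standard care = N × p × (1 - q). The ratio is 1/(1 - q), which does not depend on p.

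| q | Device | Standard care | Ratio |
|---|---|---|---|
| 0 | 12 × 0.20 = 2.4 | 2.4 × 1.00 = 2.4 | 1.00 |
| 0.10 | 2.4 | 2.4 × 0.90 = 2.16 | 1.11 |
| 0.25 | 2.4 | 2.4 × 0.75 = 1.8 | 1.33 |
| 0.50 | 2.4 | 2.4 × 0.50 = 1.2 | 2.00 |

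If the BP-removal limb is left out of the comparison, the ratio from this source is 1.00 for any q.

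**Step 3. Size of the population conflict.** Section 3.3.2 expects about 12 enrolled and 10 evaluable, so 2 planned losses. AST excludes only subjects who never had the BP placed. Among those who entered an admission, these are subjects randomized to standard care first who leave before the device is placed. If k of the losses are of this kind, the share of standard-care admissions lost is k/12:
- k = 0: 0%
- k = 1: 8.3%
- k = 2: 16.7%

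Under the 6.5.3 set, none are lost. A device-first subject who leaves after the first admission stays in both sets, so the loss runs one way.

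**The case against.** **The BP-removal limb is narrow.** Section 4.5.2 allows a return to the subject's own pump or injections only for a complete failure expected to last over an hour, and expects this to be rare by day. Section 4.9.2 turns to a backup system when BP function is in doubt and no correctable fault is found. The limb therefore mainly captures device failure. This stands: q is probably small, and nothing supports its upper range. It is also a reason to report these events as device events rather than within a between-admission comparison.

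**Other planned outputs show hyperglycemia evenly.** Section 6.2 gives time above 180 and 250 mg/dL in both admissions, section 6.4.3 counts unscheduled set replacements in both and lists technical faults, and section 7.2.2 says monitoring is the same in all arms. This also stands, and limits the harm. It does not make the AE count itself comparable.

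**The synopsis compares SAEs only, and the safety hypothesis in section 2.3 is about tolerability.** True, but section 6.5.3 explicitly extends the comparison to AEs.

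**A reader might infer that SAE counts are biased too.** Only the device admission may be extended: "Subjects will be discharged on the fourth day or afterward if the subject requires additional time to transition back". One SAE outcome in section 8.6 is that the event "requires inpatient hospitalization or prolongation of existing hospitalization". The documents do not support that inference. Section 8.6 requires an adverse experience that results in the prolongation, and a foreseen transition stay is not in itself such an experience.

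**A reader might also infer that set replacement inflates device AEs.** Section 4.5.2 asks only that replacement be considered, and section 8.5.1 still requires the episode to be prolonged. An earlier prompt does not show more qualifying events; it justifies a sensitivity display and no more.

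**Conclusion.** Two defects are confirmed in the text. First, a planned AE comparison includes a criterion that standard care cannot meet. The resulting ratio is 1/(1 - q), or 1.11 at q = 0.10 and 1.33 at q = 0.25; q is assumed, and the effect vanishes at q = 0. Second, sections 6.5 and 6.5.3 contradict each other on the safety set, with 0 to 2 of about 12 standard-care admissions at stake. Losing 2 requires every planned loss to be a standard-care-first subject who leaves before device placement.

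It would go too far to say that AE and SAE counts as a whole are not comparable, or that device AEs would double. The SAE, DKA, ketone and severe-hypoglycemia definitions apply equally in both admissions. A doubling needs q = 0.50, for which the documents give no basis. Nor does the safety population simply depend on the device, since section 6.5.3 states one that does not; the fault is the unresolved contradiction. The plan should be changed because the bias has a known direction and the correction is cheap.

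**What to change.** **Section 6.5.3.** For the between-period comparison of hyperglycemia AEs:
- leave out events that qualify only by BP removal, and report them separately as device events;
- compare on criteria that either admission can meet: ketones > 0.6 mmol/L, DKA, and prolonged hyperglycemia with set replacement;
- show the result with and without the set-replacement events, because section 4.5.2 prompts a set review earlier on the device than section 4.9.2 does.

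**Section 6.5.** Replace the AST rule for safety with the section 6.5.3 set of all subjects who entered either admission, and use the number entering each admission as its denominator.

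Section 8.5.1 need not change. Adding a home-pump counterpart to the BP-removal limb would also restore symmetry, but it would alter a rule that section 8.5.1 says was aligned with other protocols under the same device exemption.

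**Cost.** Wording in two sections. The compared hyperglycemia AE count is slightly narrower; all events are still recorded and reported under section 8.5.1, and no clinical procedure changes.
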